6.4.3.5 Best-corrected Visual Acuity

All BCVA measures will be used as safety measures to evaluate vision loss over time. BCVA is also used as a measure of efficacy as described in Section 6.4.2.1.

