8.5 Unscheduled Visits

Additional examinations may be performed as necessary to ensure the safety and well-being of patients during the study. The eCRFs should be completed for each unscheduled visit.

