2.2 Analysis Visit Windows

Analysis visit windows are defined according to study days, which are defined in Table 1.

Visit windows defined in Table 1 will be applied to all by-visit analyses of safety and treatment effect variables. Out-of-window visits (including the exit visit) and unscheduled visits will be reassigned to the visit that the actual study days fall within.

In cases where multiple visits occurred within a single visit window, which resulted in multiple data points for the same window, the last visit with non-missing data will be used for analysis.

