Other safety variables include vision loss as measured by decrease of BCVA, IOP, biomicroscopic and ophthalmoscopy findings, post-injection assessment, blood chemistry, hematology, urinalysis, physical examinations, vital signs, and urine pregnancy test outcomes.

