Summary for 4) ocular TEAEs, 6) treatment-related ocular TEAEs, and 7) TEAEs of special interest of intraocular inflammation will be sorted by preferred term in descending order. A patient with multiple occurrences of the same preferred term within the reporting period will be counted only once for that PT.

7. Interim Analyses

An interim analysis (IA) is planned when all patients have completed the Week 12 visit or have exited early from the study.

A data summary will be presented for all available cumulative data by focusing on safety especially intraocular inflammation AE rates.

8. Deviations from Protocol

This is the original analysis plan and there are no deviations from the current study protocol.

9. References

SAS/STAT User's Guide Version 9.3, SAS Institute Inc., Cary, NC

10. Amendment(s)

None.

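### The last-value-in-window rule also governs by-visit safety tables, so a transient vision loss, pressure rise or slit-lamp finding can drop out, and no readable section adds a worst-value summary

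*Protocol*

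**What the plan says.** Protocol 6.4.3.5 gives BCVA a safety role as well as an efficacy role: "All BCVA measures will be used as safety measures to evaluate vision loss over time". SAP Section 6 takes this up: "Other safety variables include vision loss as measured by decrease of BCVA, IOP, biomicroscopic and ophthalmoscopy findings, post-injection assessment" are among the non-adverse-event safety variables.

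SAP 2.2 sets the rule for by-visit tables in three steps:

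- Scope: "Visit windows defined in Table 1 will be applied to all by-visit analyses of safety and treatment effect variables".
- Placement: "Out-of-window visits (including the exit visit) and unscheduled visits will be reassigned to the visit that the actual study days fall within".
- Choice when a window holds more than one visit: "the last visit with non-missing data will be used for analysis".

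Nothing in SAP 2.2 exempts safety variables from the third step. Protocol 8.5 says of visits outside the schedule: "The eCRFs should be completed for each unscheduled visit". Findings recorded there reach the database.

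Intraocular inflammation as an adverse event follows a different path. SAP 6.2 counts each patient once per preferred term over the reporting period, takes the greater of onset and maximum severity, and states that "7) TEAEs of special interest of intraocular inflammation will be sorted by preferred term in descending order". None of that is by-visit.

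**The concern.** Scheduled visits are four weeks apart, so an acute problem between them may be examined first at an unscheduled visit. If the next examination falls in the same window and the eye has recovered, the by-visit table shows only the recovered value. For an efficacy mean this is a matter of convention. For a safety measure, the extreme is the information wanted, and the rule can discard it.

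Protocol 5.6.1 adds to this. It has patients with intraocular inflammation leave the study once the event has resolved, so their exit examination is a post-resolution one. SAP 2.2 names the exit visit among those placed by study day. When exit falls in the same window as the acute examination, the exit value is the one kept.

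The study exists to evaluate safety and treatment effect of product from a modified manufacturing process (Protocol Section 1), and the interim look centres on inflammation (SAP Section 7). The inflammation event itself will be counted. What could be lost is how many letters the eye dropped, how high the pressure went and how marked the slit-lamp findings were.

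**Working it through.** The plan states no figure that turns on this rule, and the sample size is empirical, so there is nothing to reproduce. The check traces the rule and then illustrates how often it would bite.

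**One patient.** Suppose BCVA change is -20 letters at an unscheduled visit on Day 10 and -2 letters at the scheduled visit on Day 29 (Week 4). If both days lie in the Week 4 window, SAP 2.2 keeps -2. In SAP Table 2 the patient moves from category 7 (worsening of 15 or more) to category 4 (no change). The stable-vision proportion in SAP 5.2 is also calculated visit by visit, so it does not recover the loss.

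**How often a value would be displaced.** The SAP table of windows is not readable, so the following are assumptions:

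- visits are 28 days apart and windows are cut midway, with day 14 belonging to the earlier window;
- the unscheduled visit is equally likely on days 1 to 27 after a scheduled visit;
- the variable is measured at every visit, and any later visit shows recovery.

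With no follow-up before the next scheduled visit, displacement occurs on days 15 to 27: 13/27 = 48%.

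With a recovered follow-up visit f days later (f up to 14), days 1 to 14 - f are added, giving (13 + 14 - f)/27:

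- f = 3: 24/27 = 89%
- f = 7: 20/27 = 74%
- f = 10: 17/27 = 63%
- f = 14: 13/27 = 48%

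In the remaining 11% to 52% the unscheduled value is itself the last in its window. It is then kept, and it replaces the scheduled value.

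The first interval could differ, because SAP 5.1.1 schedules no BCVA between Day 1 and Week 4. If the Week 4 window opens on Day 2, every unscheduled value on Days 2 to 28 would be displaced by a Week 4 visit (27/27). If instead it opens about Day 15, the Day 10 value above is not in it, and the example does not apply.

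**What a reader of the tables would see.** Let k of 100 patients have a transient loss of 15 or more letters, all displaced (k is assumed). The by-visit tables show 0/100. Its exact upper 95% limit is 1 - 0.025^(1/100) = 3.6%. An any-visit summary, with Clopper-Pearson limits, would show:

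- k = 2: 2% (0.2 to 7.0%)
- k = 5: 5% (1.6 to 11.3%)
- k = 10: 10% (4.9 to 17.6%)

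**Whether the adverse event tables fill the gap.** They do so in part. Protocol 9.1.3 grades severity by tolerability and interference with activity, which gives no letters lost, peak IOP or slit-lamp grade. Protocol 9.1.1 also keeps out of adverse event reporting any worsening judged unequivocally due to disease progression or lack of efficacy, unless it exceeds the expected course.

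**The case against.** Several points on the other side are sound.

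- A reader might infer that acute inflammation itself is overwritten. The documents do not support that. Inflammation is a TEAE of special interest, counted over the whole reporting period and outside the window rule. Only by-visit biomicroscopy and ophthalmoscopy tables are exposed.
- A reader might also infer that the SAP contradicts the protocol. Protocol 6.4.3.5 names no summary statistic, and its reference to change over time can be met by a by-visit display. Keeping one value per window sits uneasily with using all measures, but this is tension, not contradiction.
- Displacement is not automatic. It needs a later non-missing value in the same window, and the higher percentages above assume an early follow-up visit showing recovery. Protocol 8.5 does not say that BCVA is measured at every unscheduled visit.
- A sharp drop in vision from acute inflammation would not ordinarily meet the disease-progression exemption, so it should still be reported as an adverse event. That stands, but the report would not carry the size of the drop into a table.
- Much safety text is not public. The readable SAP names IOP, biomicroscopy and ophthalmoscopy as safety variables without giving a method for any of them, and it codes the two sets of findings in MedDRA, which would suit incidence tables. A worst-value summary may exist in a section that cannot be read. The recommendation has to be conditional on that.
- Replacing the by-visit value with the worst in each window would create a second BCVA series and is not needed. A single study-level table meets the concern.

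**Conclusion.** The point holds in limited form. As written, SAP 2.2 lets a later recovered value displace a transient BCVA loss, IOP rise or biomicroscopy or ophthalmoscopy finding in the by-visit safety tables, and no readable section restores the extreme. The SAP already takes the maximum for adverse event severity, and its measured safety variables lack a counterpart.

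The size is unknown. The 48% to 89% displacement range rests on assumed windows and assumed recovery, and the 2, 5 and 10 per 100 are assumed event counts. A reader might take these as a stated number of percentage points missing from the trial's vision-loss rate. The documents do not support that: they give neither window limits nor event rates, and the readable SAP plans no any-time vision-loss rate.

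The conclusion assumes that no non-public section already provides a worst-value summary.

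**What to change.** Keep the by-visit tables as they are. State in SAP 2.2 and Section 6 that the last-in-window rule does not limit summaries of safety extremes. Add one per-patient table for the study eye, taking the worst post-baseline value over all scheduled, unscheduled and exit visits:

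- number and percent with a BCVA loss of 15 or more letters at any time, with exact 95% CI;
- maximum IOP;
- worst biomicroscopy and ophthalmoscopy finding.

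If a non-public section already contains this, a cross-reference from SAP 2.2 is enough.

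The cost is some SAP wording and one extra table, using data already entered on the eCRFs. Safety frequencies may look slightly less favourable. Worst values also depend somewhat on how often a patient is examined, and a table footnote should say so.

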6.4.3.6 Pregnancy Test

Females of childbearing potential will have urine pregnancy tests performed at baseline (Day 1, prior to treatment administration) and study exit. Urine pregnancy test kits will be provided by the site and will be administered at the site according to the instructions provided with the tests. The pregnancy test must be negative for the patient to receive study medication. Additional pregnancy tests may be performed at any time during the study, at the investigator’s discretion.

6.4.3.7 Adverse Events

All adverse events will be monitored and reported on an adverse event eCRF, including seriousness, severity, action taken, and relationship to study drug. If adverse events occur, the first concern will be the safety of the study patient.

Approval Date: 16-Oct-2018

6.5 Other Study Supplies

Allergan will make provisions (directly or indirectly) to supply the study sites with standard photographs for grading of cataracts, ETDRS supplies (if needed), medications or supplies (anti-infective ophthalmic solution, local anesthetic eyedrop, dilating eyedrop, povidone iodine, syringe, needles, cotton tip swabs, sterile fields, and cellulose sponges), PK blood sampling kits, and immunogenicity (anti-abicipar antibody) blood sampling kits. Tubes for collection of clinical laboratory analysis will be provided by a central laboratory.

6.6 Summary of Methods of Data Collection

Clinical data will be entered into the eCRF using an electronic data capture system. Data entered into the eCRF will correspond to and be supported by source documentation maintained at the sites.

7. Statistical Procedures

This section is a summary of the planned statistical analyses. A detailed statistical analysis plan (SAP) will be developed and finalized before database lock.

7.1 Analysis Populations

The safety population, consisting of patients who received at least 1 study treatment, will be used for all analyses.

7.2 Methods of Analysis

7.2.1 Efficacy Analyses

Efficacy measures will be based on BCVA and CRT measured in the study eye. Efficacy variables include the following:

- Proportion of patients with stable vision (ie, patients who lose fewer than 15 letters in BCVA) from baseline
- Mean change from baseline in BCVA
- Proportion of patients with a gain of 15 or more ETDRS letters in BCVA from baseline

- Mean change from baseline in CRT as assessed with SD-OCT

Efficacy variables will be summarized using descriptive statistics as appropriate.

[Redacted]

[Redacted]

[Redacted]

[Redacted]

[Redacted]

7.3 Subgroup Analyses

Not applicable.

7.4 Sample Size Calculation

The study will enroll approximately 100 patients. This sample size is determined empirically and is considered appropriate for the planned assessments.

Approval Date: 16-Oct-2018

7.5 Interim Analyses

An interim analysis is planned when all patients have completed the Week 12 visit or have exited early from the study.

[REDACTED]

8.1 Patient Entry Procedures

8.1.1 Overview of Entry Procedures

Prospective patients as defined by the criteria in Sections 4.3 and 4.4 (inclusion/exclusion criteria) will be considered for entry into this study.

8.1.2 Informed Consent and Patient Privacy

The study will be discussed with the patient and a patient wishing to participate must give informed consent prior to any study-related procedures or change in treatment. The patient must also give authorization and other written documentation in accordance with the relevant country and local privacy requirements (where applicable) prior to any study-related procedures or change in treatment.

[figure not shown]
Each patient that provides informed consent and/or assent will be assigned a patient number that will be used on patient documentation throughout the study.

8.2 Procedures for Final Study Entry

[figure not shown]
All screening laboratory tests must be performed, and the results must be evaluated and determined to be acceptable to the investigator prior to patient entry into the study. Screening laboratory tests may be repeated once at the discretion of the investigator or Allergan.

A urine pregnancy test administered to women of childbearing potential at the baseline (Day 1) visit must be negative prior to treatment administration.

[figure not shown]
A patient is considered to have entered the study at the time of assignment to treatment at the baseline (Day 1) visit. See Section 5.5 for the method for assignment to treatment.

[figure not shown]
Approval Date: 16-Oct-2018

[figure not shown]
Approval Date: 16-Oct-2018

[figure not shown]
Approval Date: 16-Oct-2018

Approval Date: 16-Oct-2018

Approval Date: 16-Oct-2018

8.4 Instructions for the Patients

Patients are instructed that they do not need to fast before visits.

Patients are instructed to strictly follow the study visit schedule and to report all changes in condition to the investigative site.

8.5 Unscheduled Visits

Additional examinations may be performed as necessary to ensure the safety and well-being of patients during the study. The eCRFs should be completed for each unscheduled visit.

8.6 Compliance with Protocol

Allergan must be informed of any patients who are inadvertently enrolled despite significant deviation from protocol-specified criteria. A decision regarding the patient's continued participation will be made on a case-by-case basis.

8.7 Early Discontinuation of Patients

Patients may voluntarily withdraw from the study at any time. A patient's participation in the study may be terminated if it is deemed by the investigator or Allergan that it is unsafe for the patient to continue in the study.

Notification of early patient discontinuation from the study and the reason for discontinuation will be made to the sponsor and will be clearly documented on the appropriate eCRF.

For patients who discontinue from the study early due to other reasons, every effort must be made to have these patients return to the clinical center for completion of the Early Exit visit.

8.8 Study Termination

The study may be stopped at his/her study site at any time by the site investigator. Allergan may stop the study (and/or the study site) for any reason with appropriate notification.

9. Adverse Events

Adverse events occurring during the study will be recorded on an adverse event eCRF. If adverse events occur, the first concern will be the safety of the study participants.

9.1 Definitions

9.1.1 Adverse Event

An adverse event is any untoward medical occurrence in a patient or clinical investigation patient administered a pharmaceutical product and that does not necessarily have a causal relationship with this treatment. An adverse event can therefore be any unfavorable and unintended sign (including an abnormal laboratory finding), symptom, or disease temporally associated with the use of a medicinal (investigational) product, whether or not related to the medicinal (investigational) product. In addition, during the screening period, adverse events will be assessed regardless of the administration of a pharmaceutical product.

Note: Adverse events must be collected once informed consent has been obtained, regardless of whether or not the patient has been administered study drug.

Progression of treatment indication including new or worsening of anticipated clinical signs or symptoms, which are collected as clinical efficacy variables and assessed as unequivocally associated with the disease progression and/or lack of efficacy, should NOT be reported as

adverse events unless the disease progression is greater than anticipated in the natural course of the disease.

Adverse events will be assessed, documented, and recorded in the eCRF throughout the study (ie, after informed consent has been obtained). At each visit, the investigator will begin by querying for adverse events by asking each patient a general, non-directed question such as “How have you been feeling since the last visit?” Directed questioning and examination will then be done as appropriate. All reported adverse events will be documented on the appropriate eCRF.

9.1.2 Serious Adverse Event

A serious adverse event is any adverse event occurring at any dose that results in any of the following outcomes: death, a life-threatening adverse event, inpatient hospitalization or prolongation of existing hospitalization, a persistent or significant disability/incapacity, or a congenital anomaly/birth defect. Important medical events that may not result in death, be life-threatening, or require hospitalization may be considered a serious adverse event when, based upon appropriate medical judgment, they may jeopardize the patient and may require medical or surgical intervention to prevent one of the outcomes listed in this definition. (See Section 9.3 for procedures for reporting a serious adverse event.)

Allergan considers all cancer adverse events as serious adverse events. In addition, Allergan considers any abortion (spontaneous or nonspontaneous) as a serious adverse event.

Pre-planned surgeries or procedures for pre-existing, known medical conditions for which a patient requires hospitalization is not reportable as a serious adverse event.

Any pre-planned surgery or procedure should be clearly documented in the site source documents by the medically qualified investigator at the time of the patient’s entry into the study. If it has not been documented at the time of the patient’s entry into the study, then it should be documented as a serious adverse event and reported to Allergan.

9.1.3 Severity

A clinical determination will be made of the intensity of an adverse event. The severity assessment for a clinical adverse event must be completed using the following definitions as guidelines:

Mild	Awareness of sign or symptom, but easily tolerated.
Moderate	Discomfort enough to cause interference with usual activity.
Severe	Incapacitating with inability to work or do usual activity.
Not applicable	In some cases, an adverse event may be an ‘all or nothing’ finding which cannot be graded.

9.1.4 Relationship to Study Drug or Study Procedure

A determination will be made of the relationship (if any) between an adverse event and the study drug or study procedure, as applicable. A causal relationship is present if a determination is made that there is a reasonable possibility that the adverse event may have been caused by the drug or study procedure.

A study procedure occurring during the screening/baseline period can include a study required diagnostic procedure.

For treatment-related adverse events, the investigator will note on the eCRF whether the event is related to the study medication, and/or the injection procedure.

9.2 Procedures for Reporting Adverse Events

Any adverse event must be recorded on the appropriate eCRF.

All adverse events that are drug-related and unexpected (not listed as treatment-related in the current Investigator’s Brochure) must be reported to the governing Institutional Review Board/Independent Ethics Committee (IRB/IEC) as required by the IRB/IEC, local regulations, and the governing health authorities. Any adverse event that is marked ‘ongoing’ at the exit visit must be followed-up as appropriate.

9.3 Procedures for Reporting a Serious Adverse Event

Any serious adverse event occurring during the study period (beginning with informed consent) and for at least 12 weeks after the last dose of study drug must be immediately reported but no later than 24 hours after learning of a serious adverse event. Serious adverse events must be reported to Allergan (or Agent of Allergan) as listed on the Allergan Study Contacts Page and recorded on the serious adverse event form. All patients with a serious adverse event must be followed up and the outcomes reported. The investigator must supply

the sponsor and the IRB/IEC with any additional requested information (eg, autopsy reports and discharge summaries).

In the event of a serious adverse event, the investigator must:

1. Notify Allergan immediately by fax or email using the serious adverse event form (contact details can be found on page 1 of the serious adverse event form); phone numbers and relevant Allergan personnel contacts are also on the front page of protocol and Study Contacts Page.
2. Obtain and maintain in his/her files all pertinent medical records, information, and medical judgments from colleagues who assisted in the treatment and follow-up of the patient.
3. Provide Allergan with a complete, written description of the adverse event(s) on the serious adverse event form describing the event chronologically, including any treatment given (eg, medications administered, procedures performed) for the adverse event(s). Summarize relevant clinical information about the event: signs, symptoms, diagnosis, clinical course and relevant clinical laboratory tests, etc. Include any additional or alternative explanation(s) for the causality which includes a statement as to whether the event was or was not related to the use of the investigational drug.
4. Promptly inform the governing IRB/IEC of the serious adverse event as required by the IRB/IEC, local regulations, and the governing health authorities.

